### 6.4 Exclusion Criteria

1. Subject diagnosed with severe diaper rash
2. History of allergy or hypersensitivity to any ingredient of the test product
3. Presence of any disease or lesions near or on the area to be treated, e.g.,
  - a. Inflammation, active, or chronic infection in or near the treatment area
  - b. Psoriasis, eczema, rosacea, atopic dermatitis, herpes zoster/herpes simplex, and acanthosis
  - c. Scars or deformities

Protocol GLI.04.US.SL.023

CONFIDENTIAL

4. History of coexisting bacterial infections or medical conditions with uncontrolled gastrointestinal diseases and/or bowel movements
5. History of severe elastosis and/or excessive sun exposure that, in the opinion of the Investigator, could have affected the outcome of the study
6. Planning on having surgeries and/or invasive medical procedures during the course of the study
7. Treatment with chemotherapy, immunosuppressive agents, inhaled corticosteroids, immunomodulatory therapy (e.g., monoclonal antibodies or antiviral treatment for human immunodeficiency virus or hepatitis C)
8. Current use of topical corticosteroids, topical prescription, or oral antibiotics in the treatment area, or use within last 2 weeks
9. Current use of over-the counter topical medications for diaper rash
10. History of cancer or previous radiation near or on the treatment area
11. Human immunodeficiency virus positive or active hepatitis
12. Presence of dermal markings on or near the treatment area that, in the opinion of the Investigator, will interfere with the clinical assessments
13. Any medical condition that, in the opinion of the Investigator, would make the subject unsuitable for inclusion (e.g., a chronic or relapsing disease that may interfere with the outcome of the study)
14. Other condition preventing the subject from entering the study in the Investigator's opinion, (e.g., subjects failing baseline assessments, subjects not likely to avoid other cosmetic treatments in the treatment area, subjects anticipated to be unavailable or incapable of understanding the study assessments or having unrealistic expectations of the treatment result).
15. Study site personnel, close relatives of the study site personnel (e.g., parent/legal guardians, children, siblings, or spouse), or employees and close relatives of employees at the Sponsor company.
16. Participation in any interventional clinical study within 30 days of screening

## 6.5 Concomitant Therapies

All treatments and therapies used 30 days prior to enrollment (Visit 1) or 90 days prior to enrollment for biologics and all treatments or therapies used during the course of the study must be recorded in the Case Report Form (CRF) or electronic Case Report Form (eCRF).

### 6.5.1. Authorized Therapies

Unless listed under the exclusion criteria (see Section 6.4) or in Prohibited Therapies (see Section 6.5.2), other therapies to treat ongoing conditions are authorized.

### 6.5.2. Prohibited Therapies

None other than as specified in the Inclusion/Exclusion criteria.

The decision to administer a prohibited medication/treatment should be made with the safety of the subject being the primary consideration. Whenever possible, Galderma Laboratories, L.P.

Protocol Version: 01

This document contains confidential, proprietary information.

Protocol GLI.04.US.SL.023

CONFIDENTIAL

should be notified before the prohibited medication/treatment is administered to discuss possible alternatives.

If a subject receives prohibited therapy during the study, the subject may be allowed (at the discretion of the Investigator / Galderma Laboratories, L.P.) to continue in the study for safety evaluation purposes, only.

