Investigational Products:	Cetaphil Healing Ointment Fla#1748 (ref.:B50H48)
Treatment Area / Treatment Regimen / Mode of Administration	Healing Ointment will be applied topically to the rash area with every diaper change

Effectiveness Assessments:	
Clinical Grading
 

• Efficacy assessment of skin health, skin smoothness, skin texture compared to baseline

 
Self-Assessment Questionnaire
 

• Parent/legal guardian assessment

Safety Assessments:	
Tolerability assessment of dryness, peeling, edema
 
Safety/tolerability assessment at each visit
 
Adverse Event reporting: AEs will be obtained from signs and symptoms reported by the subject or detected during each examination.

Statistical Methods:	
In general effectiveness, safety and baseline characteristics variables will be presented using descriptive statistics within each treatment group and in combination, and graphs as appropriate. Continuous endpoints will be summarized using descriptive statistics, e.g., mean, median, standard deviation, minimum and maximum values. Categorical endpoints will be presented in frequency tables with number and percentage of observations for each level.

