## 11. SAFETY ASSESSMENTS

Safety assessments for this study include an evaluation and an interview of the subjects' parent/legal guardians at each visit to obtain information about any medical occurrence that meets the definition of an AE, and a subject diary. In addition, Investigator will perform tolerability assessment to grade the degree of irritation.

Protocol GLI.04.US.SL.023

CONFIDENTIAL

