### 12.2 Analysis Population

The following populations will be defined:

Intention-to-treat (ITT)	Includes all subjects who receive a test product. Subjects are analyzed based on the as treated principle.
--------------------------	--

Protocol Version: 01

This document contains confidential, proprietary information.

Protocol GLI.04.US.SL.023

CONFIDENTIAL

Per protocol (PP) Includes all subjects in ITT who complete the study after pre-conditioning visit without any deviations that are considered to have substantial impact on the primary effectiveness outcome.

ITT is the primary population for all effectiveness and safety analyses. The primary effectiveness analysis will be repeated using the PP analysis set if there is at least a 10% difference in the number of subjects between the PP and ITT sets.

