**Table 5. Statistical Analysis Plan**

Evaluation	Change from Baseline	Notes/Interpretation
Efficacy Grading 

Skin smoothness (tactile)

Skin texture

Diaper dermatitis

	Paired t-test; If normality fails, a Wilcoxon signed-rank test will be used.	A decrease in scores indicates an improvement
Tolerability Grading 

Dryness

Peeling

Edema

	Paired t-test; If normality fails, a Wilcoxon signed-rank test will be used.	A decrease in scores or lack of significant increase indicates tolerability/safety of the treatment product
Self-Assessment Questionnaire	N/A	Percentage of favorable and unfavorable responses will be provided for each question

Questionnaires will be tabulated; and the frequency and percentage of all response options will be reported for each question and time point. For questionnaire inquiries without baseline response data, a binomial (sign) test will be performed to test if the proportion of the combined designated favorable responses is equal to the combined designated unfavorable responses for each applicable question. A higher percentage of favorable responses with a significant *p* value indicates positive subject perceptions of the study treatment.

Protocol Version: 01

This document contains confidential, proprietary information.

Protocol GLI.04.US.SL.023

CONFIDENTIAL

A more appropriate analysis may be performed, which will be recorded in biostatistics note to file and/or in the study report.

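### The plan has no rule for tolerability scores taken after a prohibited therapy, so a treated reaction can disappear from the Table 5 test and from the percent worsened

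*Combined protocol and SAP*

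**What the plan says.** **Retention.** Section 6.5.2 defines prohibited therapies by reference: "None other than as specified in the Inclusion/Exclusion criteria". Two of the exclusion criteria in section 6.4 name products used on the graded area or for the rash itself: "Current use of topical corticosteroids, topical prescription, or oral antibiotics in the treatment area, or use within last 2 weeks" and "Current use of over-the counter topical medications for diaper rash". An infant who receives a prohibited therapy may, at the discretion of the investigator or sponsor, be allowed "to continue in the study for safety evaluation purposes, only".

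**What safety evaluation includes.** The synopsis lists "Tolerability assessment of dryness, peeling, edema" under safety assessments. Section 11 agrees: "In addition, Investigator will perform tolerability assessment to grade the degree of irritation". Section 10, however, also names tolerability grading among the methods for collecting effectiveness data.

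**Analysis.** Section 12.2 states: "ITT is the primary population for all effectiveness and safety analyses". That set is everyone who receives product. The per-protocol repeat applies only to the primary effectiveness analysis. Table 5 tests change from baseline with a paired t-test, or a Wilcoxon signed-rank test if normality fails, and gives the reading: "A decrease in scores or lack of significant increase indicates tolerability/safety of the treatment product". Section 12.4 also reports the percent of subjects improved or worsened, over the total number of subjects.

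Section 12 does not cut off, flag or separately analyse scores recorded after a prohibited therapy.

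**The concern.** The restriction to safety evaluation implies that an infant given another therapy no longer informs efficacy. Yet a topical corticosteroid or a diaper-rash product can also change dryness, peeling and edema, which are the scores that remain in use. Suppose an infant reacts to the ointment, is treated with another product between visits and is then graded at Day 7 or Day 21. The score may be back at baseline. Followed as written, the plan counts that infant as unchanged and credits the score to the ointment.

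Table 5 makes this matter more, because no decrease is needed: a non-significant increase is enough for the ointment to be read as tolerated. The clinical hypothesis in section 4.2 likewise rests on there being no significant increase at any time point. With at most 30 completers, a few scores can decide that.

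**Working it through.** The plan gives no power, standard deviation or expected reaction rate, so there is no figure of its own to reproduce. What follows is an illustration.

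**Inputs from the documents**
- Maximum 30 completers (section 6.1).
- Two-sided tests at 5% (section 12.1).
- Paired t-test or signed-rank test on change from baseline (Table 5).

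**Assumptions**
- One sign, one visit, n = 30.
- 6 infants worsen by one grade and 24 do not change.
- A treated infant returns exactly to baseline.

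**Formulas.** With k infants at +1 and the rest at 0:
- mean = k/30
- SD² = (k − k²/30)/29
- t = mean/(SD/√30), on 29 degrees of freedom
- exact signed-rank, zeros dropped and all non-zero changes equal and positive: p = 2 × 0.5^k

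**No infant treated (k = 6).** Mean 0.20; SD² = (6 − 1.2)/29 = 0.1655, SD = 0.407; t = 0.20/(0.407/√30) = 2.69.

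| Treated back to baseline | k left at +1 | Percent worsened | t-test p | Signed-rank p |
|---|---|---|---|---|
| 0 of 6 | 6 | 20.0% | 0.012 | 0.031 |
| 1 of 6 | 5 | 16.7% | 0.023 | 0.063 |
| 2 of 6 | 4 | 13.3% | 0.043 | 0.125 |
| 3 of 6 | 3 | 10.0% | 0.083 | 0.25 |

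One treated infant removes significance under the signed-rank test; three remove it under the t-test. Changes that are mostly zero would probably fail a normality check, which makes the signed-rank test the likely one.

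**Would dropping the later scores help?**
- One treated infant dropped: 5 at +1 and 24 at 0. Signed-rank p is still 2 × 0.5^5 = 0.063, because zeros were already excluded. The t-test p is 0.0225, against 0.0226 with the score kept.
- All six treated and dropped: 24 zeros remain, which Table 5 again reads as tolerated.

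Dropping therefore loses the reactors as well.

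**Would an unfavourable value help?** With the one treated infant ranked as the largest worsening, all six non-zero changes are positive and p = 2 × 0.5^6 = 0.031, the value with nobody treated. The same holds with three treated. A t-test needs an actual number: +1 for that infant gives p = 0.012, and +3, the full range of the Table 4 scale, gives p = 0.030.

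**The case against.** - **The reaction is not lost to safety reporting.** Section 13.1.2 records a local sign as a related adverse event when it leads to prescribed corrective treatment or permanent discontinuation. Section 13 reports clinically relevant worsening regardless of causality. Section 11.2 displays diary symptoms separately. This stands: a reader might infer that the reaction vanishes from the trial, and the documents do not support that. But none of these records alters the Table 5 test or the percent worsened.
- **Continuation is optional.** Section 6.5.2 says the infant may be allowed to continue, section 9.2 lists protocol violation as a reason for discontinuation, and section 7.5 lets the investigator decide whether a noncompliant subject's data are excluded. So it is not certain that such scores enter the test. But the section 7.5 decision has no criteria and is not tied to prohibited therapy, so it is not a pre-specified safeguard. Exclusion would also lose the reactor.
- **The scope is unclear.** Section 10 files tolerability grading under effectiveness, so it could be argued that safety-only continuation leaves these scores out. The synopsis and section 11 say otherwise, and the conflict is itself a reason for an explicit rule.
- **The direction is not fixed.** A reader might infer that the bias always favours the product. Section 6.4 also names inhaled corticosteroids, immunosuppressive agents and chemotherapy, which need not be given for a diaper-area sign, and nothing shows that every such therapy lowers these scores. The point is therefore confined to therapy given for a diaper-area sign.

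**Conclusion.** The point holds in limited form. Where an infant given a prohibited therapy for a diaper-area sign is allowed to continue, the plan as written counts later dryness, peeling and edema scores as evidence about the ointment. They can mask a reaction in the score test and in the percent worsened, but not necessarily in adverse event or diary reporting.

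In the illustration, one to three treated infants out of six reactors turn a significant increase into a non-significant one, depending on the test. This rests on the assumed changes; how many infants would receive such therapy is unknown.

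A reader might go further and expect a significant worsening to become a significant improvement. That would require all six reactors to be treated and all six to end a grade below baseline, hence to start at grade 1 or higher on that sign. In Table 3, peeling and edema are described only under the severe grade, which is excluded at entry, so such a reversal is plausible mainly for dryness. The conclusion does not depend on it.

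**What to change.** Add to section 12.4:
1. An infant given a prohibited therapy for a diaper-area sign counts as worsened on tolerability at every later visit.
2. In the Table 5 tolerability test, that infant receives an unfavourable value, ranked as the largest worsening in the signed-rank test. If the t-test is used, state the assigned value in advance.
3. The test on all observed scores is shown as a sensitivity analysis, and the number of such infants is reported.

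Do not adopt a test that only drops post-therapy scores.

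Section 6.5 already requires therapies to be recorded on the CRF but states neither date nor reason, so add start date and indication. Reconcile the placement of tolerability grading in sections 10 and 11.

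The cost is a few sentences in the plan, two CRF items and one extra table. The downside is that the tolerability result may look slightly less favourable. No change to care is proposed.

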## 7. STUDY TREATMENT

The term “study treatment” refers to the study products (see Section 7.1)

### 7.1 Study Product Identification and Use

Study product: Cetaphil® Healing Ointment	
Form	Opaque ointment
Mode of administration	Topical application
Formula code	1748
Formula number	B50H48
Lot numbers	To be added upon study completion
Storage and handling	Store at room temperature 15-30°C (or 59-86°F), away from sunlight

### 7.2 Study Product Accountability

Upon receipt of the study products, the Investigator or designee will conduct an inventory. In accordance with federal regulations, the Investigator must agree to keep all test article in a secure location with restricted access. Designated study personnel will provide the test article to the subjects in accordance with the protocol.

During the study, the Investigator must maintain records of study treatment dispensation and collection for each subject. This record must be made available to the study monitor for the purposes of verifying the accounting of clinical supplies. Any discrepancies and/or deficiencies between the observed disposition and the written account must be recorded along with an explanation. At the conclusion of the study, the Investigator will be responsible for returning all unused study products (i.e., Cetaphil® product) unless otherwise instructed by the Sponsor. Shipping label and cost will be provided to the Investigator by the Sponsor.

### 7.3 Method of Treatment and Product Assignment

Subjects will be numbered sequentially in the order in which they qualify for entry into the study.

### 7.4 Treatment Product Dispensing

All treatment products will be administered only to subjects enrolled in the study, at no cost to subjects, and in accordance with the conditions specified in the protocol.

Protocol Version: 01

This document contains confidential, proprietary information.

Protocol GLI.04.US.SL.023

CONFIDENTIAL

## **7.5 Treatments Compliance**

Subjects will complete a daily diary, recording treatment product applications and comment during the study. Treatment product and diaries will be dispensed to subjects at Day 0 and reviewed for compliance at Day 7 and Day 21 visits. Treatment product will be visually inspected and weighed prior to distribution at Day 0. Subjects will be instructed to return the treatment product and daily diary at Day 7 and Day 21 visits. If subjects do not return their treatment product or diary at the study visits, a verbal confirmation will be obtained for usage compliance, and it will be documented as a note to file. Any suspected noncompliance with the treatment product or study instructions will be addressed by the Investigator or clinic staff. The Investigator will determine whether a subject's noncompliance will affect the study outcome and whether the data should be excluded from statistical analyses.

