### 5. OVERALL STUDY DESIGN

This is a single-center, open-label study to evaluate the efficacy and tolerability of a Healing Ointment when used on infants with mild-to-moderate diaper rash.

Protocol GLI.04.US.SL.023

CONFIDENTIAL

Subjects and their parent/legal guardians will report to the site at baseline (day 0) visit, will be given an informed consent form, HIPAA form, photography release form, and medical history form to complete.

Subjects will be screened on the basis of the selection criteria for study qualification. Efficacy assessment (skin health, skin smoothness, skin texture), and tolerability assessment (erythema, dryness, scaling, peeling, edema) will be performed, and baseline photographs will be taken.

Subjects' parent/legal guardians will be instructed to apply the provided Healing Ointment to the groin and buttocks area at every diaper change.

Subjects' parent/legal guardians will complete Day 1 questionnaire at home. Subjects and their parent/legal guardians to return to the site at day 7 ( $\pm 3$  days) and day 21 ( $\pm 3$  days) for follow-ups.

For each follow-up visit, Investigator will perform assessments and photography. Subjects' parent/legal guardians will perform self-assessment questionnaire.

A subject and their parent/legal guardian will be involved in the study for 3 weeks. The study visits are illustrated in **Error! Reference source not found.**

Protocol GLI.04.US.SL.023

CONFIDENTIAL

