### 10.1 Clinical Grading by Investigator

Investigator will grade tactile smoothness and skin texture parameters using a 10-point Griffiths' scale where 0 = Excellent (best possible condition), 1-3 = Good, 4-6 = Fair, 7-9 = Poor (worst possible condition), as described in Table 2.

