### **15.6 Changes in Study Conduct/Amendments**

No amendment will be done for modification(s) due to change in logistical or administrative aspect of the study (e.g., change in monitors, change of telephone numbers). In such a case, the appropriate institution(s) and/or person(s) will be notified of the changes.

Modification of the protocol is prohibited without prior written agreement in the form of a protocol amendment. All amendments will be created by Galderma Laboratories, L.P. and must be approved by the IRB prior to implementation except when required to mitigate immediate safety risks or when the changes involve only logistical or administrative revisions.

Amendments may necessitate that the informed consent and other study-related material be revised. If the consent form is revised, all Subjects/subjects currently enrolled in the study may be required by the IRB to sign the approved, revised informed consent form.

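### Section 7.5 lets the outcome-grading Investigator exclude noncompliant subjects' data from any analysis, which contradicts the ITT rule in Section 12.2 and leaves the primary result open to outcome-dependent selection

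*Combined protocol and SAP*

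**What the plan says.** **Exclusion for noncompliance (Section 7.5).** The Investigator decides whether a subject's "noncompliance will affect the study outcome and whether the data should be excluded from statistical analyses". This is the section's last sentence. It has no threshold, no deadline and no second reviewer, and it does not say which analysis set it concerns.

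**Analysis sets (Section 12.2).** ITT is every subject who receives product, with no exception for noncompliance, and "ITT is the primary population for all effectiveness and safety analyses". The PP set takes ITT subjects who complete without deviations judged to matter substantially for the primary outcome. The primary analysis is repeated on PP only if the two sets differ by at least 10% in number of subjects.

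**Who grades, and how.** Section 5: "This is a single-center, open-label study to evaluate the efficacy and tolerability of a Healing Ointment". Section 10.1: "Investigator will grade tactile smoothness and skin texture parameters", and the Investigator also grades diaper dermatitis. No blinded assessor or blinded data review is described.

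**Related clauses.**
- Section 6.5.2: a subject who receives prohibited therapy may be allowed "to continue in the study for safety evaluation purposes, only", at the discretion of the Investigator or sponsor.
- Section 9.2: data collected up to withdrawal are used in the analyses.
- Section 12.4, after Table 5: "A more appropriate analysis may be performed, which will be recorded in biostatistics note to file and/or in the study report".
- Section 15.6: "Modification of the protocol is prohibited without prior written agreement in the form of a protocol amendment".

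**The concern.** The plan has no control arm. Its hypothesis (Section 4.2) is a statistically significant improvement from baseline, so the within-group p-value carries the efficacy claim. That p-value has its stated meaning only if the set of infants analysed does not depend on how they did.

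Section 7.5 gives the decision to drop data to the person who assigns the grades. The test to be applied is whether noncompliance affects the study outcome, which invites a look at that outcome. The evidence may also be soft: if product or diary is not returned, verbal confirmation is accepted. With about 30 completers, a few exclusions related to outcome could move the estimate and the p-value noticeably. A reader of the report would see an analysis labelled ITT that need not contain everyone treated.

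**Working it through.** **1. The two rules side by side.** Take one infant who received product and was judged noncompliant.

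| Rule | Consequence for that infant |
|---|---|
| Section 12.2, ITT definition | In ITT, so in every primary analysis |
| Section 7.5, last sentence | May be left out of the statistical analyses, without limit to PP |

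The plan does not say which rule prevails, so membership of the primary set is not determinate.

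**2. Can the decision follow grading?** Section 7.5 places compliance review at the Day 7 and Day 21 visits. Table 1 places efficacy grading at the same visits. No deadline is set, so a decision after the Day 21 grade is permitted. An earlier decision is permitted too.

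**3. Does the PP repeat protect?** If ITT = 30, the trigger is 0.10 × 30 = 3 subjects.
- One or two PP-only exclusions (1/30 = 3.3%, 2/30 = 6.7%) do not trigger it.
- Subjects removed from all analyses leave both sets, so they add nothing to the ITT–PP difference, however many there are.

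**4. Possible size.** The plan states no power, effect size, SD or dropout rate, so there is no planned figure to reproduce.
- Inputs from the plan: 30 completers (Section 6.1), two-sided 5% level (Section 12.1), paired t-test on change from baseline (Table 5).
- Assumptions: independent N(0,1) changes in SD units, true mean change 0, and the k least-improved infants removed before testing.
- Test: t = mean change ÷ (s/√m), with m = 30 − k. A false improvement is p < 0.05 with the mean in the improving direction. There were 40,000 simulated trials.

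| Removed (k) | False improvement | Either direction | Shift in mean (SD) |
|---|---|---|---|
| 0 | 2.6% | 5.0% | 0 |
| 1 | 6.9% | 8.1% | −0.07 |
| 2 | 13.2% | 13.8% | −0.13 |
| 3 | 21.5% | 21.8% | −0.19 |
| 4 | 31.5% | 31.7% | −0.24 |

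A five-level ordinal change gives nearly the same false-improvement rates: 6.5%, 13.0%, 21.6% and 31.0%.

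**5. What drives it.** Removing one or three infants at random keeps the two-sided error at 5.0% to 5.1%. Dependence on outcome does the damage; the smaller sample does not.

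**6. When the true effect is not zero.** Same set-up with an assumed true improvement, none removed against four removed:

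| Assumed true improvement | None removed | Four removed |
|---|---|---|
| 0.5 SD | about 75% significant | about 98% significant |
| 0.8 SD | about 99% | about 100% |
| 1.0 SD | about 100% | about 100% |

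The effect on significance therefore runs from large to negligible. The shift in the estimated mean is the same in every case.

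**The case against.** **Section 7.5 may have been meant for PP.** This is plausible, since Section 12.2 gives PP a deviation-based definition. But the sentence does not say so, and saying so costs one line.

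**Timing and direction.** A reader might infer that exclusions are made after the grades are known and favour the product. The documents do not say this. Sections 9.1.2 and 9.1.3 list product weighing and diary review before clinical grading, and a Day 7 decision would precede the Day 21 grade. A parent may also stop applying because the rash has cleared, and excluding that infant would work against the product. What stands is that decisions could follow grading and nothing prevents it.

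**Prohibited therapy.** A reader might infer that these infants leave the efficacy analysis and are mostly treatment failures. Section 6.5.2 is permissive and restricts continued participation; it does not amend the ITT set or delete earlier scores, and Section 9.2 keeps data up to withdrawal. The prohibited items come from the eligibility criteria and include treatments unrelated to rash, such as inhaled corticosteroids. Scores observed after another therapy could even flatter the product. What stands is that the handling of later scores is unstated.

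**Note to file.** A reader might infer that Section 12.4 lets the planned analysis be swapped, in breach of Section 15.6. It says another analysis may be performed and recorded, not that it replaces the planned one. Because the protocol itself allows this, a breach is only one reading. Taking the better of t-test and Wilcoxon raises the error only from 5.0% to 5.8% (normal changes), although the clause is not confined to that choice.

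**Size.** The error rates assume no true change and exclusions driven entirely by outcome. That is fair, and they are offered only as a worst case.

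**Conclusion.** The contradiction between Sections 7.5 and 12.2 is established from the text and should be resolved before analysis. As written, the primary analysis set depends on an unbounded judgement by the person who grades efficacy, and the PP repeat would not reveal it. That the Investigator is unblinded is inferred from the open-label design with a single product.

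The possible size is a false-improvement rate of roughly 7% to 31% for one to four outcome-driven exclusions among 30, against a nominal 2.5%. This rests on no true change, near-normal changes and the least-improved infants being the ones removed. With a true improvement of about 0.8 SD or more, the conclusion on significance would scarcely change, though the estimate would still be shifted. The prohibited-therapy and alternative-analysis clauses are secondary points that need clarifying.

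**What to change.** **Section 7.5.** Replace the last sentence with: *Noncompliance affects membership of the PP set only, by criteria listed in advance and applied before database lock by persons without access to the efficacy grades; all data from treated subjects stay in the ITT analysis.* Handing the decision to the sponsor is not enough in itself, because Section 15.2 sends all study data to the sponsor; the people deciding must not have seen the grades.

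**Section 12 (secondary).** Reconcile Section 6.5.2 with Sections 9.2 and 12.2 by stating that subjects who receive prohibited therapy remain in ITT, with a numeric rule for their later scores. Counting them as not improved serves the percent-improved summary but gives no score for the mean-change test. One workable rule is a primary analysis on all observed scores, with a sensitivity analysis that carries baseline forward from that point (zero change).

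**Section 12.4 (secondary).** State that the planned paired t-test/Wilcoxon analysis is always reported as primary, and that any other analysis chosen after data are seen is labelled post hoc.

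**Cost.** A few sentences, a short list of PP criteria and a named person without access to the grades. No extra visits or infants are needed. The estimated improvement may be slightly less favourable.
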